### **6.3 OPTIONAL PFS-S SUB-STUDY**

An optional 12-week sub-study aiming to evaluate the usability of pre-filled syringe with safety system (PFS-S) will be conducted in some countries. Patients enrolled in LTS11210 at selected sites in those countries may participate in the PFS-S sub-study from Week 24 of the main study after providing written informed consent for the sub-study. However, patients may continue to participate in the main trial without participating in the PFS-S sub-study if they wish. Full details of the PFS-S sub-study are presented in [Appendix R](#).

### **6.4 STUDY COMMITTEES**

#### **6.4.1 Data Monitoring Committee**

A Data Monitoring Committee (DMC) is in place for the sarilumab clinical study program. The sarilumab DMC monitors the safety of the patients participating in all ongoing sarilumab studies. The DMC is responsible for giving appropriate recommendations to the Sponsor on safety aspects during the conduct of the study, if needed. In addition to the review of serious adverse events with fatal outcome and specific adverse events, the DMC has access to complementary safety parameters (eg, vital signs, laboratory test results etc.) and access to limited efficacy data. The DMC responsibilities and the data review processes are fully described in the sarilumab DMC charter.

Members of the DMC will be independent of those performing the study, being neither investigators nor employees of the Sponsor; and without conflict of interest regarding study outcome (whatever they are).

#### **6.4.2 Cardiovascular Adjudication Committee**

An independent Cardiovascular Adjudication Committee (CAC) has been established for the sarilumab clinical study program. The role of the CAC is to apply uniform criteria for the evaluation of cardiovascular events (including retrospective events), and to adjudicate these events in a consistent and unbiased manner throughout the course of the study. The goal of the CAC is to ensure that cardiovascular events reported by the site are judged uniformly, using the same criteria by a group of experts in cardiology and neurology, independent from Sanofi. The CAC will be blinded to treatment allocation. The CAC responsibilities, detailed definitions of

cardiovascular events to be adjudicated and the adjudication processes are fully described in the CAC Charter and/or Manual of Operations.

## **7 SELECTION OF PATIENTS**

### **7.1 NUMBER OF PATIENTS PLANNED**

Approximately 2000 male and female patients with RA are planned to be included.

### **7.2 INCLUSION CRITERIA**

I 01. Patients with RA who were randomized:

- in the study EFC11072 (a randomized, double-blind, placebo-controlled study in patients with active rheumatoid arthritis who are inadequate responders to MTX therapy)
  - and who have completed Part A (12 weeks) or Part B (52 weeks) of the study EFC11072.
  - or patients randomized in Part B of EFC11072 to a treatment arm subsequently not retained following pivotal dose selection.
- in the study ACT11575 and completed the treatment period.
- in the study EFC10832:
  - and completed the 24-week study treatment period.
  - or patients from 12 weeks onward with per protocol defined lack of efficacy
- in the study SFY13370 and completed the treatment period.
- in the study EFC13752 and completed the treatment period.

I 02. Patients must give informed consent for participating in the study LTS11210 prior to any procedure related to the study.

### **7.3 EXCLUSION CRITERIA**

#### **Exclusion criteria related to the mandatory background therapies**

- E 01. Patients not willing to continue to take folic/folinic acid 5 mg weekly or greater (based on local recommendations) when using MTX.
- E 02. Deleted
- E 10. Patients rolling over from ACT11575, EFC11072, EFC10832, SFY13370 studies unwilling to continue the same background DMARD therapy as received in the initial study. Patients rolling over from EFC13752 study unwilling to continue sarilumab treatment without any background DMARD therapy.

- E 12. Treatment with any DMARD other than those allowed per protocol (see [Section 8.8](#)) and limited to the maximum specified dosage.

**Exclusion criteria related to the Sanofi compound:**

- E 03. Any patient who experienced an adverse event leading to permanent discontinuation from a prior study.

E 04. Deleted

E 05. Deleted

E 06. Pregnant or breast-feeding women.

- E 07. Women of childbearing potential (WOCBP) not protected by highly-effective contraceptive method(s) of birth control (as defined in the informed consent form and/or in a local protocol addendum), and/or who are unwilling or unable to be tested for pregnancy.

*(For UK patients: Women of childbearing potential, unwilling to utilize adequate contraception methods or not become pregnant during the full course of the study. Adequate contraceptive measures include:*

- *Placement of an intrauterine device (IUD) or intrauterine system (IUS).*

*Barrier methods of contraception: Condom or Occlusive cap (diaphragm or cervical/vault caps) with spermicidal foam/gel/film/cream/suppository. The use of barrier contraceptives should always be supplemented with the use of a spermicide.*

- *Male sterilisation (with the appropriate post-vasectomy documentation of the absence of sperm in the ejaculate).*
- *True abstinence: When this is in line with the preferred and usual lifestyle of the subject. [Periodic abstinence (e.g., calendar, ovulation, symptothermal, post-ovulation methods) and withdrawal are not acceptable methods of contraception].)*

E 08. Deleted

E 09. Deleted

- E 11. Patients with an abnormality(ies) or adverse event(s) that per investigator judgment would adversely affect patient's safety and/or participation of the patient in the study.

E 13. Patients with temporary IMP discontinuation lasting > 31 days at the time of the planned first dose in the LTS11210 study.

E 14. Patients fulfilling the protocol-defined criteria for the permanent treatment discontinuation.

## 8 STUDY TREATMENTS

### 8.1 INVESTIGATIONAL MEDICINAL PRODUCT

- Pharmaceutical form: the pharmaceutical form of sarilumab has been modified since the initial version of the study protocol. Sarilumab, in vials (formulation C1F2), was dispensed to all patients enrolled into the study prior to the phase 3 dose selection decision. Thereafter, drug product in vials has been phased out of the study, and patients have been dispensed with drug product in prefilled syringes (pivotal formulation C2F3) once sufficient quantities were available and appropriate local approvals obtained. For completeness, all IMP formats used during the study are presented here:
  - Currently dispensed IMP for all patients:
    - Sarilumab in prefilled syringe (PFS): Glass syringes with a 27 gauge thin wall, 1/2-inch staked needle, with FM30 needle tip cap (latex free) filled at 1.14 mL with C2F3 drug product at 131.6 mg/mL (150mg dose) or 175 mg/mL (200mg dose). PFS with FM30 needle tip is the only pharmaceutical form dispensed to patients from EFC10832, SFY13370, and EFC13752.
    - Sarilumab in prefilled syringe with safety system (PFS-S) with exactly the same formulation as the PFS with FM30 needle tip cap described above. The PFS-S is used for patients in the sub-study only. Refer to [Appendix R](#) for further details of the safety system.
  - Previously dispensed IMP:
    - Sarilumab in amber glass vials: filled to 2 mL with 75 mg/mL (150mg dose), or 100 mg/mL (200mg dose) of C1F2 drug product
    - Sarilumab in PFS: Glass syringes as described above, but with FM27 rubber needle shield (needle cap may contain dry natural rubber latex)

To ensure that the administration of the investigational product with PFS will minimally deliver the targeted doses of 150 mg and 200 mg, the PFS will contain an 8% average overfill.

- Dose per administration
  - Before the phase 3 pivotal dose regimens were selected:**
    - 150 mg administered weekly or every other week (reduced dose)
  - After the phase 3 pivotal dose regimens were selected:**
    - 200 mg administered every other week or 150 mg administered every other week (reduced dose).
- Route and method of administration: Subcutaneously in abdomen, thigh or upper arm.

Each drug administration requires one single injection. It is preferred that subcutaneous injection sites be rotated between the four quadrants of the abdomen (except the navel or waist area) or the thigh (front and side). If needed, SC injection can be administered by a caregiver in the upper arm (lateral side).

Subjects and/or their non-professional caregivers will be trained to prepare and administer study drug at the start of the double blind-treatment period of the previous study. This training must be documented in the subject's study file. The study staff should review the subject's self-administration technique at Visit 2 or V1/V2 (Week 0) for the LTS11210 study. For doses not given at the study site, diaries will be provided to record information pertaining to those injections. If the subject is unable or unwilling to administer study drug, arrangements must be made for a qualified site personnel or a caregiver to administer study drug doses that are not scheduled to be given at the study site.

The IMP administration should be taken strictly every 14 days as per protocol IMP administration schedule, however an IMP administration time window of  $\pm 3$  days is permitted in exceptional circumstances (eg, the result of a repeat CBC test is not available, or an ongoing adverse event). For the subsequent IMP administration the initial IMP administration schedule should be followed again.

Note: an interval of at least 11 days between 2 IMP doses must be maintained.

## 8.2 NON INVESTIGATIONAL PRODUCTS

For patients rolling over from EFC11072, ACT11575, EFC10832, and SFY13370:

All patients should continue to receive the non-biologic DMARD(s) background therapy that they were receiving in the initial study until the end of study treatment. However, at any time the DMARD(s) dose can be reduced, temporarily or permanently discontinued, or a patient may switch to alternate approved non-biologic DMARD for safety or tolerability reasons. If the new DMARD is initiated the dosing as well as safety monitoring should follow the applicable local labeling information.

Each non-biologic DMARD will be recorded throughout the study on the e-CRF. Any change should be recorded on the e-CRF. DMARD(s) will not be dispensed or supplied by the Sponsor as an investigational product.

All patients receiving MTX as their background DMARD will also receive folic/folinic acid (5 mg weekly or greater) according to local guidelines in the country where the study is conducted.

For patients rolling over from EFC13752:

Treatment with non-biologic DMARDs is not allowed. All patients should continue with sarilumab monotherapy until the end of study treatment. The IMP should be permanently discontinued if any DMARD is initiated.

### **8.3 DELETED**

### **8.4 METHOD OF ASSIGNING PATIENTS TO TREATMENT GROUP**

This is an open-label study and every patient will receive sarilumab. Treatment kit numbers will be allocated via interactive voice/web response system (IVRS/IWRS). Patients will keep the same identification number that they were allocated in the previous study.

### **8.5 PACKAGING AND LABELING**

The investigational products will be supplied in treatment kit boxes that are labeled in accordance with the local regulatory specifications and requirements and content information, dosing instructions and precautionary statement (“for clinical use only”).

The number of treatment kits allocated to the patient will provide sufficient medication until the next clinic visit. An additional treatment kit, to provide medication to randomized patients in circumstances, e.g., a damaged kit, will be allocated by IVRS if a “replacement call” is made to the IVRS system.

Each IMP unit will be labeled in accordance with the local regulatory requirement.

### **8.6 STORAGE CONDITIONS AND SHELF LIFE**

All investigational drug supplies must be kept refrigerated in appropriate, secure area (for example, a locked cabinet or a locked room) under the responsibility of the Investigator or other authorized individual and must be stored separately from other medication and in the original carton as per specification mentioned on the label.

### **8.7 RESPONSIBILITIES**

The Investigator, the Hospital Pharmacist, or other personnel allowed to store and dispense IMP will be responsible for ensuring that the IMP used in the clinical trial is securely maintained as specified by the Sponsor and in accordance with the applicable regulatory requirements.

All IMP shall be dispensed in accordance with the Investigator's prescription and it is the Investigator's responsibility to ensure that an accurate record of IMP issued and returned is maintained.

Any quality issue noticed with the receipt or use of an IMP (deficiency in condition, appearance, pertaining documentation, labeling, expiration date, etc) should be promptly notified to the Sponsor. Some deficiencies may be recorded through a complaint procedure.

A potential defect in the quality of IMP may be subject to initiation of a recall procedure by the Sponsor. In this case, the Investigator will be responsible for promptly addressing any request made by the Sponsor, in order to recall IMP and eliminate potential hazards.

Under no circumstances will the Investigator supply IMP to a third party, allow the IMP to be used other than as directed by this Clinical Trial Protocol, or dispose of IMP in any other manner.

### **8.7.1 Access to the randomization code during the study**

This section is not applicable for the study.

However, in the case of a medically urgent situation, and if the Investigator (first contact person) cannot be reached, a competent medical professional can call a 24-hour emergency number provided by the Sponsor in order to get further information on the study or for medical questions.

## **8.8 CONCOMITANT MEDICATION**

A concomitant medication is any treatment received by the patient at the same time as any IMP(s). All medication taken during the study should be recorded on the corresponding pages of the e-CRF including any change in dose.

### **8.8.1 Prohibited concomitant medication**

- Use of any biologic treatment for RA is not authorized during the study until 6 weeks following the EOT visit. If any of these treatments are used, the study treatment should be permanently discontinued.
- Treatment with non-biologic DMARD(s) (such as cyclosporine, sulfasalazine, hydroxychloroquine, or cyclophosphamide) other than the DMARD(s) received in the initial study (ie, study immediately preceding LTS11210 enrollment) is not permitted until the end of treatment unless a change to an alternate approved non-biologic DMARD is made for safety or tolerability reasons. If the new DMARD is initiated the dosing as well as safety monitoring should follow local labeling information. For EFC13752 patients, the treatment with non-biologic DMARD(s) is not authorized until the end of the treatment. See [Section 8.2](#) for additional details.
- Treatment with tofacitinib or any other JAK inhibitor is not authorized during the course of the study. If any of these treatments are used, the patient should be discontinued.
- Administration of any live (attenuated) vaccine is contraindicated (see list in [Appendix K](#)) until 3 months following the last study drug administration.
- Treatment with any investigational medicinal product other than sarilumab is not permitted.

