	
Specific serum samples will be taken during the study to test for anti-drug antibody to sarilumab at week 12, every 12 weeks thereafter through year 2 and then every 24 weeks until the end of treatment and at the Post-Treatment follow-up visit 6 weeks after the end of treatment.
 
Serum samples to store for future biomarker analyses will be collected at the initial visit, week 2, 12, and 48 (except for EFC13752 patients). Whole blood to store for future ribonucleic acid (RNA) expression analysis will be collected at week 0 (baseline) and week 2, except for patients from study SFY13370 and EFC13752.
 
There will be a 6-week post treatment observation period for patients with early discontinuation and for patients who completed the planned treatment period. In patients who complete sarilumab treatment per protocol in countries where sarilumab is commercially available the post treatment follow-up visit may be cancelled if the patient initiates treatment with commercial sarilumab during the post treatment follow-up period. However, in this case, a telephone contact must be established with the patient to capture all AEs occurring up to the 1st administration of commercial sarilumab.

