### 6.2 DURATION OF STUDY PARTICIPATION

The IMP will be administered for 264 weeks from the first IMP administration in LTS11210. In addition the patients will continue to be treated beyond 264 weeks until sarilumab is commercially available in their country or until 2020 at the latest when the study will be closed. (*In the UK the duration of treatment will be 264 weeks from the first study drug administration in LTS11210*).

The total maximum duration of study participation for a patient may be up to 523 weeks.

- 1-week screening period if applicable
- 516-week maximum treatment period in LTS11210 (for the earliest patients enrolled in LTS11210 in 2010 if sarilumab is not commercialized by 2020)
- 6-week follow up period as required per protocol

Further explanation is given below and in [Section 12.1](#).

Patients will either enter a 1-week screening period (patients from EFC11072 Part A or Part B1 and ACT11575), or enrol directly into the treatment period (for patients from EFC11072 Part B2, EFC10832, SFY13370, or EFC13752 the EOT visit in the initial study corresponds to the randomization visit in the LTS11210 study).

The duration of the treatment period in the study will be at least 264 weeks, or up to a maximum of 516 weeks (*except in the UK where the duration of treatment will be 264 weeks*).

Patients will return for the safety follow-up visit 6 weeks after the EOT visit. In case of early treatment discontinuation, patients are required to complete the EOT visit and to return for the

6-week safety follow-up visit as well. In patients who complete sarilumab treatment per protocol in countries where sarilumab is commercially available the post treatment follow-up visit may be cancelled if the patient initiates treatment with commercial sarilumab during the post treatment follow-up period. However, in this case, a telephone contact must be established with the patient to capture all AEs occurring up to the 1st administration of commercial sarilumab.

The study will be considered completed for a patient at the time he/she completes all the scheduled procedures as described in [Section 12.1](#).

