### **12.1.13 Visit 50: Post Treatment safety follow-up visit**

Patients that discontinued prematurely before the planned end of treatment, or who completed their treatment per protocol should have this visit performed 6 weeks from end of treatment visit with the following exception:

- In patients who complete sarilumab treatment per protocol in countries where sarilumab is commercially available the post treatment follow-up visit may be cancelled if the patient initiates treatment with commercial sarilumab during the post treatment follow-up period. However, in this case, a telephone contact must be established with the patient to capture all AEs occurring up to the 1st administration of commercial sarilumab.

The Investigator will:

- Record vital signs including body temperature, blood pressure and HR and weight.
- Perform tuberculosis assessment. In case of suspicion of tuberculosis, refer the patient to a TB specialist for complete examination and additional work-up (see specific instructions in [Section 10.2.1](#)).
- Inquire regarding AE/SAEs and concomitant medications.
- Obtain urine for pregnancy test for female of child bearing potential.
- Obtain serum sample for PK (sarilumab) and for anti-sarilumab antibody.

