#### ***Observation period***

The observation period will be divided into 4 epochs:

- The SCREENING epoch is defined as beginning with the last visit in the previous studies to the first dose of IMP in LTS11210
- The TREATMENT epoch is defined as the time from first dose of IMP in LTS11210 to last dose of IMP + 13 days (6 days for patients receiving weekly injections only)
- The FOLLOW-UP epoch is defined as the time from the end of TREATMENT epoch to last dose of IMP + 60 days
- The POST-STUDY epoch is defined as the time after the last dose of IMP + 60 days

The rationale of having “last dose of IMP + 60 days” as the end of follow-up epoch is to capture the events observed within an approximately 5 half-lives of the last IMP. The treatment-emergent AE (TEAE) period will include both TREATMENT and FOLLOW-UP epochs.

Please note: Not all the patients will have all 4 epochs. For example, if a patient died on the 7th day after the last dose of IMP, his/her TREATMENT epoch will be from the first dose of IMP to his/her death date and will have no FOLLOW-UP or POST-STUDY epoch; if a patient had his last visit (i.e. follow-up visit 29) on the 50th day after the last dose of IMP and have no AE reported after this date, his/her FOLLOW-UP epoch will be ended on last dose of IMP+50 days and will have no POST-STUDY epoch.

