##### ***Pharmacokinetic variables***

All the PK analyses will be performed using the PK population.

Serum samples will be analyzed for functional SAR153191 concentrations using validated enzyme-linked immunosorbent assay (ELISA) methods with a targeted lower limit of quantitation (LLQ) of 0.294 mg/L (*REGN88-AV-07026-SA-01V1*) or 0.3125 mg/L (*REGN88-AV-13131-VA-01V1*). Serum concentrations of functional sarilumab will be summarized using arithmetic and geometric means, standard deviation (SD), standard error of the mean (SEM), coefficient of variation (CV%), minimum, median and maximum by actual dose and visit. Concentrations below LLOQ were replaced by LLOQ/2.

After the completion of EFC11072 (Mobility) Part B study, the Sponsor made the decision to discontinue measurement of bound sarilumab concentration from ongoing studies globally. Serum concentrations of bound sarilumab (serum sarilumab-sIL-6R $\alpha$  complex) will not be summarized in this study.

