For PK, ADA and Vital signs, the follow-up (ie, 6-week post-treatment) measurement will be defined based on the sample collected at the follow-up Visit 50.

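### Protocol 8.8.1 bars every RA biologic until 6 weeks after EOT although completers are expected to start commercial sarilumab then, and SAP 2.5.4 would label a switcher's Visit 50 PK/ADA sample as post-treatment (minor inconsistency)

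*Protocol*

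**What the plan says.** Protocol 8.8.1 lists prohibited concomitant medication. Its first bullet reads: "Use of any biologic treatment for RA is not authorized during the study until 6 weeks following the EOT visit". The stated consequence of use is permanent discontinuation of study treatment. The bullet contains no exception.

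Protocol 6.2 addresses patients who complete treatment per protocol in a country where sarilumab is marketed. For them, "the post treatment follow-up visit may be cancelled if the patient initiates treatment with commercial sarilumab during the post treatment follow-up period", and a telephone contact then collects adverse events up to the first commercial dose. The same provision stands in the Clinical Trial Summary, in footnote a of both flow charts (1.2.1 and 1.2.2), in 12.1 and in 12.1.13. The SAP repeats it in footnote a of its own flow charts (1.4.3.1 and 1.4.3.2).

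If Visit 50 is held, 12.1.13 instructs the site: "Obtain serum sample for PK (sarilumab) and for anti-sarilumab antibody". No condition refers to commercial use. The visit also includes this step: "Inquire regarding AE/SAEs and concomitant medications".

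SAP 2.5.4, in the line after Table 6, covers PK, ADA and vital signs: "the follow-up (ie, 6-week post-treatment) measurement will be defined based on the sample collected at the follow-up Visit 50". On the PK analysis, SAP 2.4.6 says: "Serum concentrations of functional sarilumab will be summarized using arithmetic and geometric means". It also replaces values below the lower limit of quantitation by half that limit.

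**The concern.** Sarilumab is itself a biologic for RA, and commercial product is not study drug. Read literally, 8.8.1 therefore forbids what six other places in the protocol plan for. This exit route is not rare by design: under 12.1, commercial availability in the patient's country is one of the main triggers for a completer's EOT visit. A site that consulted only the prohibited-medication section could tell a completer to wait 6 weeks, or could log a deviation that was never intended.

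The analysis consequence is separate. The post-treatment PK and ADA measurement is meant to describe patients about 8 weeks after their last study dose. A switcher who still attends Visit 50 contributes a sample taken on drug, and SAP 2.5.4 assigns the label by visit number alone. That is a wrong classification under a stated rule, although it arises only in that situation.

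**Working it through.** **Comparison of the texts**

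1. Window of the ban: from study start to EOT + 6 weeks (8.8.1).
2. Window in which commercial sarilumab is foreseen: the post-treatment follow-up period, EOT to EOT + 6 weeks (6.2, 12.1.13). The two coincide over those 6 weeks.
3. Visit 50 may be cancelled but need not be. A cancelled visit gives no sample. A held visit gives PK and ADA samples (12.1.13).
4. SAP 2.5.4 maps any Visit 50 sample to the post-treatment value. SAP 2.1.3, 2.3.3, 2.4.6, 2.4.8 and 2.5.4 contain no exclusion or flag for samples taken after a first commercial dose.

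The misclassification follows from steps 3 and 4 without any arithmetic. The plan gives no figure to reproduce.

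**Illustration of size**

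Inputs:
- Half-life: SAP 2.1.3 justifies the 60-day limit as capturing events "within an approximately 5 half-lives of the last IMP", so 60 / 5 = 12 days.
- Last study dose 14 days before EOT (assumed; range 11 to 17, from the 14 ± 3 day dosing rule in 8.1).
- Visit 50 at EOT + 42 days (± 3, flow chart).
- Commercial sarilumab every 14 days at the study dose (assumed).
- First-order elimination, with each dose counted in full at once (assumed).
- The replacement rule for values below the quantitation limit is ignored.

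Time since last study dose at Visit 50: 14 + 42 = 56 days (11 + 39 = 50 to 17 + 45 = 62).

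Set the steady-state level just after a dose to 1. Over one interval the level falls to r = 2^(-14/12) = 0.445, so each dose adds 1 - r = 0.555.

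Off-drug level: 2^(-56/12) = 0.039.

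Switcher's level for a first commercial dose on day s after EOT: 0.039 + 0.555 × sum of 2^(-(42 - d)/12) over dosing days d = s, s + 14, ... before day 42.

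Worked case, s = 28: 0.555 × 2^(-14/12) = 0.247; 0.247 + 0.039 = 0.286; ratio 7.3.

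| Start day s | Commercial doses before day 42 | Days since latest dose | Level | Ratio to off-drug |
|---|---|---|---|---|
| 0 | 3 | 14 | 0.445 | 11.3 |
| 7 | 3 | 7 | 0.648 | 16.5 |
| 13 | 3 | 1 | 0.900 | 22.9 |
| 14 | 2 | 14 | 0.396 | 10.1 |
| 27 | 2 | 1 | 0.796 | 20.2 |
| 28 | 1 | 14 | 0.286 | 7.3 |
| 41 | 1 | 1 | 0.563 | 14.3 |

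(Ratios are computed from unrounded levels.)

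Over every start day from 0 to 41 the smallest ratio is 7.3 (day 28) and the largest 22.9 (day 13). Letting the gap before EOT run from 11 to 17 days and Visit 50 from day 39 to 45 widens this to about 5 to 34.

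**The case against.** The strongest reply is that a specific provision overrides a general one. The commercial switch is covered in six places, including the section a site follows for Visit 50. The sanction in 8.8.1, stopping study treatment, has no effect after EOT. Section 8.8 defines concomitant medication as treatment given alongside study drug, and 11.2.1 stops treatment for biologics other than study drug, so the target is probably other biologics. Most of this stands and keeps the 8.8.1 half small. It does not remove the conflict, because the first bullet of 8.8.1 expressly covers the 6 weeks after EOT. It is also true that the six places say what happens to Visit 50 if a patient switches; permission is implied and not worded as an authorization.

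On the SAP half, three things must coincide: a switch within 6 weeks, a visit that is not cancelled, and a sample drawn after the first commercial dose. The documents give no frequency, and it could be zero. That also stands.

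On the size, the quantitation-limit rule could change the off-drug value 8 weeks after dosing, so the ratios are not predictions of observed data. A range of 7 to 11 would be too narrow even within this model: it holds only for starts on day 0, 14 or 28, when the sample falls at a trough.

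The ADA effect cannot be sized. SAP 2.4.8 classifies ADA status over the whole treatment-emergent period, with only the titer plot shown by time point.

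**Conclusion.** A minor internal inconsistency, with one wrong classification under a stated analysis rule. Both halves rest on the text alone. Only the illustrative ratio of about 7 to 23 depends on the modelling assumptions listed above.

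Three stronger readings are tempting, and the documents do not support them:

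- A reader might infer that the protocol really forbids completers to move to commercial sarilumab. Provisions that plan for a first commercial dose in that window make this implausible.
- A reader might infer that the Visit 50 mean concentration is inflated by a calculable factor. That needs the share of Visit 50 samples that come from switchers, which appears nowhere, and the effect of the quantitation-limit rule, so no inflation figure is given.
- A reader might infer that the primary safety endpoint is compromised. The rule at issue governs the labelling of a Visit 50 measurement. Where the visit is cancelled, the telephone contact still collects adverse events up to the first commercial dose. Nothing here establishes an effect on adverse-event counts or person-time.

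**What to change.** Two edits.

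- Protocol 8.8.1, first bullet, add: *except commercial sarilumab started after the EOT visit by patients who completed treatment per protocol (see 6.2, 12.1, 12.1.13).*
- SAP 2.5.4, add: *A Visit 50 PK or ADA sample drawn on or after the day of the first dose of commercial sarilumab, or when commercial sarilumab use is recorded with a start date too incomplete to show the sample preceded it, is excluded from the 6-week post-treatment summary and listed separately.*

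The clause on incomplete dates is needed because SAP 2.5.3 does not impute medication dates. No new data are required: Visit 50 already includes a concomitant-medication inquiry, and 8.8 has all medication taken during the study recorded in the e-CRF. The cost is a few fewer Visit 50 samples in the summary, plus a clause and a sentence of text.
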